2.6 Overview and Rationale of Study Design

The SHARP study is a single-center open-label, Phase 2 clinical trial of stereotactic body radiation therapy (SBRT), hormone/androgen deprivation therapy (ADT) and radium Ra 223 dichloride for participants with newly diagnosed oligometastatic castration sensitive prostate cancer.

Eligibility

Participants will be adults diagnosed with metastatic prostate adenocarcinoma who have undergone full treatment at the primary prostate site. Participants will be chemotherapy naïve to metastatic sites, unless exposure occurred during treatment for primary disease.

Oligometastatic burden will be limited to a maximum of four lesions, consistent with a summary analysis demonstrating improved prognosis for SBRT in prostate cancer for participants with four or fewer lesions [22]. In addition, participants must have at least one bone lesion to increase benefit over any risk from the bone specific radium Ra 223 dichloride regimen.

Participants must have at least one bone lesion and each non-visceral lesion (bone and lymph node) should not exceed more than 5 cm. In addition, participants may have one lung lesion (< 2cm); no liver lesions are permitted.

Treatment program

The treatment program is comprised of SBRT, administered over the first cycle, radium Ra 223 dichloride administered over 6 cycles, and concurrent standard of care ADT (luteinizing hormone-releasing hormone agonist-either leuprolide or goserelin, or LHRH antagonist degarelix or relugolix). Each treatment cycle is 28 days.

Participants will be receiving ADT for approximately 36 weeks as part of this study (can be started prior to consent) to increase radiosensitivity [23, 41]. Metastatic prostate cancer patients often present at COH having initiated standard of care ADT. Therefore, there is no benefit derived from monitoring patients during their initial single-agent standard of care ADT.

Typically standard of care ADT is continued indefinitely however it is associated with side effects of fatigue, hot flushes, erectile dysfunction, muscle loss, osteoporosis and sometime “drug holidays” are given. Thus, ADT will be discontinued after a total of 36 weeks and participants will be monitored carefully. We hypothesize that some patients may achieve long-term remission off ADT, however upon disease recurrence ADT (and other appropriate standard treatment) will be resumed.

Around initiation of protocol therapy, participants will also be required to take bisphosphonate or RANKL inhibitor bone health agents at the dose and schedule consistent with the treatment of bone metastases or prevention of osteoporosis. Participants will continue this regimen until they have reached testosterone recovery, or at the discretion of the PI.

SBRT

SBRT (dosing administered minimum every 40 hours from Day 1 over 7-21 days during Cycle 1). The dose of SBRT will be 9Gy x 3 fractions to bone metastases and 5Gy x 5 fractions to lymph node metastases respecting normal tissues tolerances. Dose constraints will be similar to previous radiation therapy oncology group trials and multiple papers detailing stereotactic body radiation therapy (SBRT). Normal tissue constraints based on previous published multi-institutional trials and on the national physics guidelines set forth by AAPM task group 101 [42]. Primarily our dose constraints will be based on NRG-BR001 and previous published RTOG trials: RTOG 0236, 0813, 0915, 0438, 0613. These other RTOG trials

already looked at safe SBRT doses for lung, liver, spine and bone metastases. Per previous established SBRT protocols each separate oligometastatic site will have its own separate isocenter. Of note ongoing SBRT trial STOMP dose escalates to 10Gy x 3 fractions but does not allow for the concurrent use of ADT or include radium Ra 223 dichloride [24]. NRG BR001 also dose escalates based on tumor metastasis site from 10Gy x 3 fractions to 15Gy x 3 fractions or 10Gy x 5 fractions if central structures and allows concurrent use of ADT (NCT02206334). Other published studies have documented efficacy of 9Gy x 3 fractions and this is Dose Level -1 for the ongoing SBRT trials and thus we have chosen this as the starting SBRT dose level for the bone metastases.

Patients with asymptomatic low volume locoregional recurrent disease will be allowed to enroll on this study after discussion with the PI. In the case where the low volume recurrence is amenable to SBRT, it will be included in the SBRT treatment. In the case where the low volume recurrence is not amenable to SBRT based on reirradiation risk, then we will follow these lesions with re-imaging scans and reassess at later time points for further local control, which will be allowed on study. Additionally, if these patients fail only at the untreated site (due to the untreated recurrence/disease not being amenable to SBRT) they will be censored in the primary efficacy analysis at that time. Patients with high risk disease in which salvage radiation to the prostate bed is recommended in the absence of lesions noted on scans will be allowed to enroll after discussion with the PI. In these cases, salvage radiation to the prostate bed may occur at the same time as the SBRT.

Radium Ra 223 dichloride will be administered during ADT therapy based on the knowledge of general synergy between ADT and radiation therapies in the treatment of prostate cancer. Radium Ra 223 dichloride has been developed as a treatment given concurrently with ADT therefore safety of that combination has been established. The purpose of radium Ra 223 dichloride therapy is to enhance anticancer effect against known oligo bone metastases required for eligibility for this study, but also treatment of likely invisible bone micrometastases. Laboratory tests will be monitored every 4 weeks and general guidelines for administration of Radium 223 will be followed. These include: for the 1st dose of Radium 223 baseline laboratory test need to be: Hgb \geq 9.0 g/dL, ANC \geq 1,500 cells/mm³, platelets \geq 100,000 cells/mm³. For subsequent infusions (2-6) there is no Hgb requirement, ANC \geq 1,000 cells/mm³, platelets \geq 50,000 cells/mm³.

Up to 7 cycles of protocol therapy are planned in the absence of unacceptable toxicity or disease progression, whichever comes first. If one agent is discontinued due to toxicity, then the participant may continue to receive the other protocol therapy agent(s).

In addition to capturing efficacy endpoints, participants will undergo follow-up up to 5 years to capture long term toxicities (e.g. secondary malignancies) due SBRT and/or radium Ra 223 dichloride.

Efficacy

Prostate-specific antigen (PSA) assessments will occur every cycle during protocol therapy and then every 3 months during Response Follow-up to mimic the ongoing STOM trial [24]. Tumor evaluation will occur pre-SBRT and then at the post Ra-223 visit (post-6 doses of radium Ra 223 dichloride), and during Response Follow-up (every 6 months and at PSA progression).

This study will assess response via PSA levels alone and also use combined PSA and tumor evaluations per the modified Prostate Cancer Working Group 2 criteria [43]. Time to treatment failure will be a primary efficacy endpoint.

Correlative Tumor Studies

Genomic alterations in prostate cancer are being extensively studied although majority of data pertains to metastatic castration resistant prostate cancers (mCRPC) and primary tumors, with relative scarcity of information regarding metastatic hormone sensitive sites. Approximately 90% of mCRPC patients harbor

clinically actionable molecular alterations. Alterations in androgen receptor (AR) signaling pathways, ETS genes, TP53, and PTEN are reported in about 40-60% of patients. Other genomic alterations include *PIK3CA/B*, *RSPO*, *RAF*, *APC*, β -catenin, and *ZBTB16*. Germline and somatic alterations in DNA repair genes gathered significant attention because of potential implications for sensitivity to PARP inhibitors and platin chemotherapy. 23% of mCRPC patients harbor DNA repair pathway aberrations (BRCA2, BRCA1, ATM) and 8% harbor germline findings [44]. Exploratory biomarker analysis on baseline pre-SBRT archival and fresh tissue will be performed. A prostate cancer biomarker panel (e.g. Foundation One platform) will be utilized to analyze genomic alterations in metastatic prostate cancer prior to development of castration resistance.

Correlative Blood Studies

The purpose of the blood correlatives of the study is to assess *in-vivo* effects of radiation on expression of proteins related immune suppression in patients with metastatic prostate cancer. Circulating immune cell populations and plasma levels of cytokines, chemokines and growth factors will be assessed. From this data, we will be able to determine the feasibility of conducting future first-in-human studies involving pathway-specific and novel immunotherapeutic agents for this disease site.

Alkaline Phosphatase Normalization Studies

Alkaline phosphatase levels will be monitored during the study. Increased serum alkaline phosphatase is associated with progression of bone metastases and may predict disease progression and death [21]. The protocol regimen may suppress bone metastases and lead to normalization of alkaline phosphatase levels at the end of protocol therapy in participants with elevated levels of alkaline phosphatase at baseline.

3.0 ELIGIBILITY CRITERIA

Patient MRN	Patient Initials (F, M, L):
-------------	-----------------------------

Participants must meet all of the following criteria on screening examination to be eligible to participate in the study:

3.1 Inclusion Criteria

Informed Consent and Willingness to Participate

- __1. Documented informed consent of participant and/or Legally Authorized Representative.
- __2. Agreement to provide archival primary or metastatic tumor tissue if available

Age Criteria, Performance Status, and Life Expectancy

- __3. Age: ≥ 18 years
- __4. ECOG ≤ 2 ([Appendix A](#))
- __5. Life expectancy > 12 months

Nature of Illness and Treatment History

- __6. Histologic diagnosis of prostate adenocarcinoma.
Pure small cell carcinoma will be excluded, however component of neuroendocrine /small cell differentiation will be allowed provided that adenocarcinoma constitutes majority of the tissue specimen.
- __7. Stage M1. See [Appendix B](#).

Metastatic disease can be documented by bone scan or computed tomography (CT) scan or MRI or PET/CT or the combination of these tests.
- __8. Up to 5 metastatic lesions:

Must have at least 1 bone lesion, **AND** each non-visceral lesion should be less than 5 cm

Visceral lesions will be limited to one lung lesion ($< 2\text{cm}$) or one lymph node; no liver lesions allowed. Lymph nodes allowed provided they are not in a field of prior radiation, and if amenable to SBRT (to be reviewed by PI). (note: locoregional recurrence is not considered a “visceral metastatic lesion”. This is discussed more below in #11)
- __9. Two lesions can be in close proximity (i.e. within 5cm of each other) if they meet radiation SBRT normal tissue toxicity requirements.
- __10. *If have untreated primary prostate cancer:* Must undergo debulking prostatectomy at discretion of treating urologist or definitive radiation therapy. Definitive radiation fields to include close proximity lymph nodes at discretion of treating radiation oncologist. Definitive radiation dose at discretion of treating radiation oncologist (see #14 below: for patients presenting with untreated prostate primary along with oligomets, ADT may begin concurrently with the definitive radiation, for a total of approximately 36 weeks duration)

Patient MRN

Patient Initials (F, M, L):

__11. If had prior treatment to the prostate primary (definitive radiation therapy or prostatectomy, and can include salvage radiation to the prostate bed +/- lymph nodes), no evidence of locally persistent or recurrent prostate cancer on digital rectal exam (DRE) OR imaging studies (CT or MRI).

- Note: patients with asymptomatic low volume locoregional recurrent disease will be allowed to enroll on this study after discussion with the PI. In the case where the low volume recurrence is amenable to SBRT, it will be included in the SBRT treatment. In the case where the low volume recurrence is not amenable to SBRT based on reirradiation risk, then we will follow these lesions with re-imaging scans and reassess at later time points for further local control. Additionally, if these patients fail only at the untreated site (due to the untreated recurrence/disease not being amenable to SBRT) they will be censored in the primary efficacy analysis at that time.

__12. Does not have castration resistant disease

- Castration resistance defined as progression of disease despite serum testosterone level of <50 ng/dL

__13. PSA \geq 0.2 prior to start of androgen deprivation treatment

PSA value:

Date:

__14. Patients will be receiving approximately 36 weeks of ADT as part of this trial. The 36 weeks of ADT may start prior to consenting to this study. The patient may join the study at any point of the 36-week period of ADT treatment.

- Only Luteinizing hormone-releasing hormone (LHRH) agonist/antagonist treatment is considered ADT; bicalutamide or other antiandrogens used alone do not count.

Patient MRN	Patient Initials (F, M, L):
-------------	-----------------------------

___15. Patients must be willing to receive bisphosphonate or RANKL inhibitor bone health agents at the dose and schedule consistent with the treatment of bone metastases or prevention of osteoporosis, starting approximately from when the patient begins protocol therapy, until the patient's testosterone reaches normal levels or at the discretion of the PI. Patients who are already on a bone health agent separate from the protocol may continue on this treatment regimen and will not be required to start treatment with an additional bone health agent.

___16. Patients may have received prior hormone therapy at the discretion of the PI. Patients may have received prior targeted therapy in the context of definitive therapy.

___17. Patients may have had one prior systemic non-chemotherapeutic treatment (i.e. immunotherapy, receptor tyrosine kinase inhibitor, antiangiogenic agent, differentiating agent) for recurrent or metastatic disease.

___18. Must have refused standard of care treatment for metastatic disease

___19. Recovered from all acute side-effects (except alopecia) related to previous systemic therapy

Clinical Laboratory Criteria (To be performed within 14 days prior to Day 1 of protocol therapy)

___20. ANC \geq 1,500/mm ³ NOTE: Growth factor support is not permitted to normalize baseline ANC parameters, however subsequent growth factor administration is permitted as standard supportive care.	ANC:	Date:
___21. Platelets \geq 100,000/mm ³ NOTE: Transfusion of blood products are not allowed to normalize baseline blood parameters, however subsequent transfusions are allowed per standard supportive care guidelines.	Plts:	Date:
___22. Hemoglobin (Hgb) \geq 9.0 g/dL NOTE: Transfusion of blood products are not allowed to normalize baseline blood parameters, however subsequent transfusions are allowed per standard supportive care guidelines	Hgb:	Date:
___23. Total serum bilirubin \leq 2 x ULN	ULN: Bil:	Date:
___24. AST \leq 2.5 x ULN	ULN: AST:	Date:
___25. ALT \leq 2.5 x ULN	ULN: ALT:	Date:
___26. Creatinine \leq 2.5 mg/dL	Serum Cr:	Date:

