Email:[contact]

Co-Investigator

[name]
Dept. of Medical Oncology
T:[contact] [name]
Email:[contact]

EXPERIMENTAL DESIGN SCHEMA

Phase 2 single-arm,
open-label, single center study

*Protocol therapy lasts for 7 cycles of therapy/completion of ADT, until unacceptable toxicities or disease progression, whichever comes first.

** Stopping rules will be implemented after 2 cycles of radium 223 dichloride if unacceptable toxicity rate is $\geq 33\%$.

PROTOCOL SYNOPSIS**Protocol Title**

A Phase 2 Trial of Radium Ra 223 Dichloride in Combination with Androgen Deprivation Therapy and Stereotactic Body Radiation Therapy for Patients with Oligometastatic Castration Sensitive Prostate Cancer (SHARP)

Study Detail

Population/Indication(s):	Prostate adenocarcinoma
Phase:	Phase 2
Sample Size:	24 evaluable patients
Estimated Accrual Duration:	48 months
Estimated Study Duration	~8 years
Participant Duration:	68 months (~8 months of treatment + 60 months follow-up)
Participating Sites:	City of Hope Duarte, CA
Study Agents:	Androgen deprivation therapy, radium Ra 223 dichloride, stereotactic body radiation therapy
Sponsor:	City of Hope
Industry Partner:	Bayer
Industry Partner Protocol Number:	IIR-US-2016-1801

Rationale for this Study

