- To assess overall survival, complete response rate, duration of response, and duration of overall complete response and duration of stable disease in patients with oligometastatic castration sensitive prostate cancer who initiated the protocol regimen of ADT with SBRT and radium Ra 223 dichloride.
- To assess long-term toxicities during 5-year follow-up in patients with oligometastatic castration sensitive prostate cancer who initiated the protocol regimen of ADT with SBRT and radium Ra 223 dichloride and received at least one dose of radium Ra 223 dichloride

Exploratory Objective

- To perform exploratory analysis of primary or metastatic tumor mutation patterns in this study population at baseline
- To identify immune system factors in the blood that change during the course of ADT-radiotherapy for metastatic prostate cancer
- To describe the rate of normalization of the total alkaline phosphatase level (defined as a return to a value within the normal range) at the end of protocol therapy in patients oligometastatic castration sensitive prostate cancer with total alkaline phosphatase values above the upper limit of the normal range at baseline
- To analyze the patients who were in consideration for the study and the reason for ineligibility, including radiographic review, PSA value, and treatment window.

Study Design

The SHARP study is a single-center open-label, Phase 2 clinical trial of stereotactic body radiation therapy (SBRT), hormone/androgen deprivation therapy (ADT) and radium Ra 223 dichloride for participants with metastatic castration sensitive prostate cancer.

Participants will initiate ADT (LHRH agonist leuprolide or goserelin, or LHRH antagonist degarelix or relugolix) for 4 weeks and then receive 32 weeks of ADT on protocol for a total of 36 weeks. Concurrent with standard of care ADT on protocol participants will receive 1 cycle of SBRT followed by 6 cycles of radium Ra 223 dichloride. SBRT is limited to ≤ 4 metastatic lesions with at least 1 bone lesion. Treatment cycles will be 28 days. Participants will receive bisphosphonate or RANKL inhibitor bone health agents at the dose and schedule consistent with the treatment of bone metastases or prevention of osteoporosis, starting approximately when the protocol therapy is initiated and ending when the patient reaches testosterone recovery (>50 ng/dL) or at the discretion of the PI.

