5.3 Treatment Plan

The treatment plan is as follows ([Table 5.3](#)). Participants must already have received at least 28 days of ADT (leuprolide OR goserelin OR degarelix OR relugolix) **prior** to initiating Cycle 1 Day 1 SBRT. While on protocol therapy, participants must also receive bisphosphonate or RANKL inhibitor bone health agents at the dose and schedule consistent with the treatment of bone metastases or prevention of osteoporosis, until their testosterone levels reach the normal range or at the discretion of the PI.

Stopping rules may be implemented if there is unacceptable toxicity. For further details see [Section 13.0](#)

Table 5.3 Treatment Regimen and Schedule

Agent/Therapy and Route of Administration	Dose	Timing of administration and planned duration
Stereotactic Body Radiation Therapy (SBRT) via External Beam Radiation via TrueBeam Stx	9Gy x 3 fractions (bone) 5Gy x 5 fractions (lymph node) 10Gyx5 (lung)	Cycle 1 Day 1, then dosing administered minimum every 40 hours over 7 to 21 days during Cycle 1
Radium Ra 223 dichloride via Slow IV over 1 minute	55 kBq/kg	Cycles 2-7 Day 1 of each 28-day cycle
Leuprolide OR goserelin OR degarelix OR relugolix Per package insert/investigator discretion		Starting at least 4 weeks prior to SBRT and continuing for a total of 36 weeks as part of regimen on protocol

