5.4 Agent Administration

5.4.1 Androgen deprivation therapy

Luteinizing hormone-releasing hormone (LHRH) agonists consisting of either leuprolide OR goserelin OR LHRH antagonist degarelix OR relugolix will be administered per package insert and investigator discretion.

Participants will receive in total 36 weeks of therapy with a LHRH agonist/antagonist; starting at least 28 days prior to initiating Cycle 1 Day 1 stereotactic body radiation therapy.

There is no requirement that the same LHRH agonist/antagonist (whether leuprolide or goserelin or degarelix or relugolix) be administered for the duration of the study.

Dose delay guidelines are described in [Section 6.3](#).

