5.4.3 Radium Ra 223 dichloride

Participants will receive 6 cycles of Radium Ra 223 dichloride following completion of SBRT.

Participants **must meet criteria** in [Section 6.2](#) to receive the **first dose** of radium Ra 223 dichloride.

Radium Ra 223 dichloride will be administered as a slow bolus intravenous injection over 1 minute by a trained physician.

The volume of radium Ra 223 dichloride to be administered to a given participant should be calculated using the:

- Participant's body weight (kg)- calculated **within 30 days** of the dosing day
- Dosage level 55kBq/kg body weight
- Radioactivity concentration of the product (1,100 kBq/mL; 30 microcurie/mL) at reference date
- Decay correction factor to correct for physical decay of Radium Ra 223 dichloride
 - Radium-223 is an alpha particle emitter with a physical t_{1/2} of 11.4 days.

$$\text{Volume to be administered (mL)} = \frac{\text{Body weight in kg} \times 55 \text{ kBq/kg body weight}}{\text{Decay factor} \times 1,100 \text{ kBq/mL}}$$

Before administration of radium Ra 223 dichloride, the participant must be well hydrated; the participant should be instructed to drink ad libitum.

For additional information regarding administration and preparation refer to [Section 9.1](#).

Prophylactic treatment for nausea and vomiting is not recommended. For supportive care guidelines refer to [Section 5.9](#).

For dose delays due to treatment-related toxicity refer to [Section 6.2](#).

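### Inclusion #14 sets no latest start within the 36-week ADT course, but six radium doses fit inside that course only if Cycle 1 Day 1 is by about ADT week 12, and Table 6.1 contradicts #14 on timing

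*Combined protocol and SAP*

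**What the plan says.** Entry. Inclusion #14 in section 3.1, repeated in the synopsis, sets ADT at approximately 36 weeks, allows it to begin before consent, and adds: "The patient may join the study at any point of the 36-week period of ADT treatment".

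Lead-in. Table 5.3 describes ADT as "Starting at least 4 weeks prior to SBRT and continuing for a total of 36 weeks as part of regimen on protocol", and section 5.4.1 has it "starting at least 28 days prior to initiating Cycle 1 Day 1 stereotactic body radiation therapy". Both give a minimum interval before SBRT and no maximum.

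Concurrency. The synopsis (Study Design) says "Concurrent with standard of care ADT on protocol participants will receive 1 cycle of SBRT followed by 6 cycles of radium Ra 223 dichloride". Section 2.6 says "Radium Ra 223 dichloride will be administered during ADT therapy", giving ADT-radiation synergy as the reason and treating the safety of the combination as established. Section 2.6 also says "ADT will be discontinued after a total of 36 weeks".

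Radium course. Section 5.4.3: "Participants will receive 6 cycles of Radium Ra 223 dichloride following completion of SBRT". Section 5.2 places the doses on Day 1 of Cycles 2 to 7. Section 5.6 lists completion of seven cycles among the reasons to end protocol therapy and does not list the end of ADT. Section 5.1 and calendar footnote c (section 11.0) also end at seven cycles. A footnote to the Experimental Design Schema is looser: "Protocol therapy lasts for 7 cycles of therapy/completion of ADT".

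Start criteria. In Table 6.1, a patient who misses row 1, 2, 3 (neutrophils, platelets, hemoglobin) or 5 (ADT-related adverse events) must permanently stop protocol therapy if SBRT cannot begin by 28 (+7) days after the first ADT dose. Patients who began ADT together with radiation or surgery are excepted. Table 6.2 counts its 28-day allowance from the planned radium dose instead.

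**The concern.** The trial tests a three-part regimen in which radium is given under ADT. #14 admits patients for whom the rest of the schedule cannot deliver that. A late starter who follows section 5.6 receives some radium after the planned ADT stop, outside the rationale in section 2.6. With 24 evaluable patients, a few such cases would blur which regimen the result describes.

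The primary endpoint is also touched. Table 12.1 starts time to treatment failure (TTF) at ADT initiation, while section 13.2 makes a patient evaluable for efficacy only after at least one dose each of SBRT and radium. #12 excludes castration-resistant disease. A late joiner therefore brings in a stretch of failure-free time on ADT that precedes any radium.

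Table 6.1 is a separate problem. Its clock starts at the first ADT dose, so it may already have run out when a patient admitted under #14 reaches C1D1.

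**Working it through.** **Inputs.** ADT total of 36 weeks (synopsis; 2.6). Radium on Day 1 of Cycles 2 to 7 (5.2). Cycle length 28 days (5.2), with a window of ±7 days (calendar footnote d). Delay of up to 28 days for a radium dose (Tables 6.2 and 6.3). Table 6.1 limit of 28 (+7) days.

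**The plan's own timeline.** The synopsis has 4 weeks of ADT and then 32 on protocol: 4 + 32 = 36. With C1D1 at week 4, radium falls at weeks 8, 12, 16, 20, 24 and 28. All six doses are within ADT, with 36 − 28 = 8 weeks to spare.

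**General case.** Let C1D1 be at ADT week w, with 4-week cycles. Dose k falls at week w + 4k, so dose 6 is at w + 24. A dose at week 36 is counted as within ADT.

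- All six doses within ADT: w + 24 ≤ 36, so w ≤ 12.
- With one 28-day delay: w + 28 ≤ 36, so w ≤ 8.
- Post-radium visit, 28 days after dose 6, still within ADT: w + 28 ≤ 36, so w ≤ 8.

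| C1D1 (ADT week) | Radium doses by week 36 | ADT weeks needed to cover dose 6 (w + 24) |
|---|---|---|
| 4 | 6 | 28 |
| 12 | 6 | 36 |
| 16 | 5 | 40 |
| 20 | 4 | 44 |
| 28 | 2 | 52 |
| 32 | 1 | 56 |

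After week 32 no dose falls within ADT.

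**Table 6.1.** 28 + 7 = 35, so the limit is ADT day 35. It can be read in two ways.

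- As a general cap for non-exempt patients, C1D1 is by week 5 and dose 6 is at 5 + 24 = week 29. The regimen then fits inside ADT, but #14, which admits at any point, is contradicted.
- As a recovery window for an unmet criterion, a non-exempt patient past day 35 has no days left. One transient miss of row 1, 2, 3 or 5 ends protocol therapy, even if the blood-count criteria #20 to #22 were met within the previous 14 days.

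Rows 4 and 6 do not use this clock.

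**Lead time in TTF.** The first radium dose is at w + 4 weeks after the TTF origin: week 8 for w = 4, week 16 for w = 12, week 32 for w = 28. Between the first and last of these the difference is 24 weeks, or 24 × 7 / 30.4 = 5.5 months for that patient. The benchmark median in section 13.5 is 16 months. The effect on the trial's median cannot be computed without the distribution of entry times.

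**The case against.** The strongest reply is that a latest start already exists. Table 6.1 describes its limit as a constraint on time and grants an exception to it, which suggests a general rule, and an exploratory objective in section 1.3 names the treatment window as a reason for ineligibility. On that reading non-exempt patients start by week 5 and late starts are confined to the exempt group. This is a fair reading, but the limit sits in the column for unmet criteria, and if it is general it contradicts #14 outright. A wording conflict remains either way.

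The reply continues that 36 weeks is approximate, that three-month depots may hold testosterone down after the nominal stop, and that entry after starting ADT is deliberate because patients often arrive already on it (2.6). All of this stands as mitigation. It does not stretch to the 44 or 52 weeks needed for a start at week 20 or 28.

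Some stronger inferences are tempting and are not supported:

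- From the schema footnote, a reader might infer that radium stops with ADT, so that late joiners get fewer than six doses. Sections 5.6 and 5.1 and calendar footnote c all end therapy at seven cycles. The footnote is loose wording.
- From the ±7-day window, a reader might quote a limit of week 18 (36 − 6 × 3) down to week 6 (36 − 6 × 5). Those ends need every cycle to run at 21 or at 35 days. The window is scheduling tolerance, and week 12 is the nominal figure.
- #10 lets ADT begin with definitive prostate radiation, and section 2.4 places that before Cycle 1. A reader might infer that this route passes week 12. No duration is given. Assuming 74 Gy (a dose cited in 2.4) in five weekly fractions of 1.8 to 2 Gy, radiation takes about 7.4 to 8.2 weeks, which can leave C1D1 inside week 12.

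**Conclusion.** The conflict is real and sits in the current text. #14 sets no latest C1D1, while six radium doses fit within 36 weeks of ADT only for C1D1 by about week 12, or week 8 with one permitted delay. This assumes 28-day cycles and a stop at week 36. Under section 5.6, later starters would receive one to six radium doses after ADT. Table 6.1 either contradicts #14 or denies non-exempt joiners past ADT day 35 any recovery time.

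The size in patients is unknown, because the documents give no distribution of entry times. The effect on response is uncertain, since testosterone may stay suppressed after the nominal stop. No shift in the TTF median or in the 25-month threshold has been shown. This is a correctable inconsistency in the regimen definition with a possible lead-time effect on the primary endpoint, and it does not show that the trial's result would be wrong.

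**What to change.** 1. In Table 6.1, count the recovery window from planned C1D1, as Table 6.2 does from the planned dose, and keep the exemption for radiation or surgery. This is a wording change.

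2. In #14, 5.3, 5.4.1 and the synopsis, choose one rule. Either state a latest C1D1 of about ADT week 12 (week 8 to leave room for one delay), or state that ADT continues through the last radium dose for later starters. The cap narrows entry for remaining accrual. Extending ADT keeps entry open but departs from the 36 weeks of ADT in the historical trial behind the 16-month benchmark: a start at week 20 needs 44 − 36 = 8 extra weeks. A week-12 cap does not put the post-radium visit on ADT, since that visit falls at 12 + 28 = week 40; week 8 would. Align the schema footnote with section 5.6.

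3. For all enrolled patients, tabulate weeks from ADT start to C1D1, radium doses given within ADT, and testosterone at the post-radium visit. Report TTF from C1D1 as a descriptive sensitivity analysis beside TTF from ADT start, with no formal subgroup comparison in 24 patients. This uses treatment dates and the testosterone values already scheduled in the study calendar, so the cost is one table and one extra estimate.
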